In this 3-arm randomized controlled trial (RCT), parent-child dyads will be assigned to a 10-week group-based intervention, delivered to parents, targeting adolescent substance use prevention and diet improvement through parenting and family-focused strategies. The proposed study will be conducted in partnership with our longtime research collaborator, the ADA. ADA has a demonstrated record of successfully recruiting and retaining thousands of Mexican heritage and other Latino parents into *Realizing the American Dream* (RAD), their academic success program with no substance use prevention or nutrition content. ADA's trained community facilitators will lead the parents' groups (15 parents per group) via three conditions: substance use prevention and healthy nutrition (FPNG+; n=498 parent-child dyads); substance use prevention only (FPNG; n=498 parent-child dyads), or a comparison condition (RAD; n=498 parent-child dyads). The three curricula will be delivered through ADA programming, offered to families of 6th – 8th grade students (11-14 years old) in 18 different schools (6 per condition). Randomization will occur at the school level, each school randomly assigned to one of the three conditions. Participants will be consented for the specific condition their school is randomized to (i.e. the consenting materials will only describe the condition the school is assigned to).

Participant recruitment

We will recruit parent-child dyads consisting of one parent and one youth enrolled in 6th, 7th or 8th grade. Following inclusiveness policies from our community partner, the American Dream Academy (ADA), parents of children enrolled in other grades will also be included if interested in the program, but their children will not be part of the study. Inclusion criteria are as follows:

Youth:

- ages 11-14
- enrolled in 6th-8th grade at the time of recruitment from the ADA programs

Adults:

- age 18 or older
- parent/caregiver/guardian of an eligible youth or parent of a child enrolled in participating schools who expresses interest in the program

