We will provide ADA with general “invitation scripts” to be used by the trained operators of the ADA phone call center describing the study and inviting parents and their children to attend an information session. Parents will be asked to bring their middle school grade child to the information session they attend. The next step in recruitment will be more targeted and will consist of phone calls to 6th-8th grade parents in an effort to maximize the number of participants with children in the target grades (6th, 7th, 8th). The ADA phone call center operators will read the script to parents according to the random assignment of each recruitment site. During the information session, trained bilingual study staff will provide an explanation of the study and answer questions prior to obtaining written consent. Parent-child dyads who are interested in participating will be asked to stay at the end for a consenting session during which the consent form will be read and explained, questions will be asked, and written consent, parental permission, and child assent will be collected. All parents of 6th, 7th, or 8th grade students will be asked to give their adolescent permission to participate in the study (data collection only). In addition, each youth will be invited to assent to each of the procedures, in addition to and separate from parental permission. We will not collect data from children who are not in 6th, 7th or 8th grades, even if their parents participate in the study. Participants will be enrolled in the study for approximately 8 months to allow for data collection and delivery of a 10-week intervention of individual workshops of 2.5 hours each. All data will be collected at baseline (T1), immediately post-intervention (T2), and at approximately 16 weeks post-intervention (T3). It is anticipated that a noteworthy majority of youth and adult participants will represent minority populations.

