Power calculations considered design effects related to the clustering of outcome means by school sites. The total estimated sample size is 1494 parent-child dyads, across 18 schools. Based on data from the FPNG effectiveness trial, the level of clustering is low for our outcomes, including an intraclass correlation equal to 0.01, a student level R-square of 0.25, and a school level R-square of 0.03.² Because the effect size for substance use outcomes ($d=0.20$; FPNG vs. C) is lower than the expected effect size for nutrition outcomes ($d=0.78$; prior non-related intervention study), the total sample size is calculated for substance use outcomes. Accounting for these parameters, the power of this design is 0.802. For the subsample, the estimated sample size is 126 households across 18 schools – 7 per school. The average effect size of .69 is calculated based upon prior work on home food availability of vegetables, fruits, and desserts. Given the above stated parameters, the power of this design is 0.814.

All analyses will be conducted using multilevel analyses in Mplus,²⁷ with families clustered within schools. This analysis accounts for the clustering which, if uncorrected, may result in biased standard errors.²⁸ All analyses will employ a robust maximum likelihood estimator to adjust for any non-normality in the distributions of outcomes and to best control for Type I errors.²⁹ The analyses will also utilize full-information maximum likelihood (FIML)³⁰ to conduct intent-to-treat analyses that account and adjust for attrition and any item missing data.

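### The power of 0.802 is stated for 1494 dyads with no attrition allowance, so power for the T3 contrasts is not given and would be lower than at 1494

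*Combined protocol and SAP*

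**What the plan says.** The Study design section sets the arm sizes, for example "substance use prevention and healthy nutrition (FPNG+; n=498 parent-child dyads" and "comparison condition (RAD; n=498 parent-child dyads", with randomisation by school "in 18 different schools (6 per condition". Three arms of 498 make 1494, or 1494/18 = 83 dyads per school.

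The power paragraph of the Data Analysis Plan uses the same total: "The total estimated sample size is 1494 parent-child dyads, across 18 schools". Its inputs are "the effect size for substance use outcomes ($d=0.20$; FPNG vs. C" and the clustering parameters, "including an intraclass correlation equal to 0.01, a student level R-square of 0.25, and a school level R-square of 0.03". It reports a power of 0.802. It does not give alpha, sidedness, the contrast or a retention rate.

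The next paragraph of that section expects loss: full-information maximum likelihood (FIML) is to "conduct intent-to-treat analyses that account and adjust for attrition and any item missing data". The last assessment is "at approximately 16 weeks post-intervention (T3", which follows a 10-week programme. The analysis compares FPNG+ with FPNG and with the comparison arm, at T2 and then at T3, adjusting for the T1 value. The mediation models end at T3.

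**The concern.** The number entering the arms and the number in the power statement are the same, and retention is not among the listed parameters. On a plain reading, 0.802 describes a trial in which every dyad gives an outcome.

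FIML keeps incomplete dyads in the model and can limit bias, but it does not restore lost outcomes. In the regression of T3 on condition and T1, a dyad without a T3 value adds essentially nothing to the T3 contrast. The long-term contrasts would then rest on fewer dyads than the power statement shows, and a null T3 result could be read against an 80% figure that was not calculated for T3.

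**Working it through.** **Inputs from the documents.** d = 0.20, ICC = 0.01, student R² = 0.25, school R² = 0.03, 18 schools (6 per arm), m = 83 dyads per school.

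**Assumptions.** Alpha 0.05, two-sided unless noted. Loss by T3 of 10-30%, spread evenly over schools. Dyads without T3 contribute nothing. The d of 0.20 is given for FPNG v comparison; it is carried over to the FPNG+ contrasts because no other value is given for substance use.

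**Formula.** With J schools in the contrast and a share P of them in one group:

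V(m) = ICC(1 − R²school) + (1 − ICC)(1 − R²student)/m

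SE = √{V(m) / [P(1 − P)J]}, noncentrality = d/SE, t reference with J − 2 df, or normal.

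V(83) = 0.01 x 0.97 + 0.99 x 0.75/83 = 0.00970 + 0.00895 = 0.01865.

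**Step 1: reproduce 0.802.** There is no unique reproduction, because alpha, sidedness and contrast are not stated. At 83 per school:

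| Basis | Power |
|---|---|
| 18 schools as two equal groups, t16 | 0.831 |
| Same, normal | 0.874 |
| Same, normal, without the R-squares | 0.817 |
| 12 v 6 schools, t16 | 0.785 |
| 12 v 6 schools, normal | 0.834 |
| 6 v 6 schools, one-sided, normal | 0.814 |
| 6 v 6 schools, normal | 0.718 |
| 6 v 6 schools, t10 | 0.629 |

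Three of these (0.785, 0.814, 0.817) fall within 2 points of 0.802; none equals it.

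**Step 2: cost of attrition if 0.802 is correct at full follow-up.** Under the normal reference, 0.802 corresponds to a noncentrality of 2.809. Divide this by √[V(m)/V(83)]:

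| Loss | m | V(m)/V(83) | Power |
|---|---|---|---|
| 10% | 74.7 | 1.053 | 0.781 |
| 20% | 66.4 | 1.120 | 0.756 |
| 30% | 58.1 | 1.206 | 0.725 |

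The cost is about 2, 5 and 8 points. It is modest because the school term, which loss of dyads does not change, is more than half of the variance (0.00970 of 0.01865).

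**Step 3: the planned contrasts, 6 v 6 schools.** Here P(1 − P)J = 0.25 x 12 = 3. At m = 83, SE = √(0.01865/3) = 0.0788 and the noncentrality is 0.20/0.0788 = 2.54. At 20% loss, V = 0.02088, SE = 0.0834 and the noncentrality is 2.40.

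| Loss | t10 | Normal |
|---|---|---|
| 0% | 0.629 | 0.718 |
| 10% | 0.607 | 0.696 |
| 20% | 0.581 | 0.669 |
| 30% | 0.550 | 0.637 |

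At full retention the gap to 0.802 is already 17 points (t10) or 8 points (normal). A 20% loss adds about 5 points.

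**The case against.** A reader might infer that 0.802 cannot hold at T3 on any basis. The documents do not support that. With all 18 schools as two equal groups, the plan's own parameters keep power at 0.802 or above up to about 14% loss (t16) or 32% (normal); 12 v 6 schools with the normal reference keeps it up to about 15%. These are not contrasts the plan sets out, and an equal two-group split does not match a 6:6:6 allocation. But the basis of 0.802 is unstated, so they cannot be excluded as its source.

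A reader might also infer that the sponsor assumed complete follow-up. That is not stated either. On the two-group t16 basis, 71-72 dyads per school (1278-1296 in all, about 86% of 1494) give 0.801-0.804, so 0.802 could in principle already contain an allowance. Nothing in the text mentions one, however, and the text attaches 0.802 to 1494.

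Two further points stand. No retention figure supports any particular loss: the Study design section credits the community partner with a good record of retaining parents in its own programme, but gives no rate for research follow-up. And FIML can recover some information where T2 is observed and in the model. The losses above are therefore close for the T3-on-T1 regression, but upper bounds for the latent-change and mediation models.

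**Conclusion.** The point holds as a gap in the power statement. No attrition allowance is shown, although attrition is expected and T3 is tested. Power for the T3 contrasts is therefore not given, and on any one basis it would be lower than the power at 1494. How far it falls depends on retention, alpha, sidedness and contrast, none of which is stated.

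The 2-8 point cost over 10-30% loss depends on 0.802 being right at full follow-up, so the resulting values of 0.73-0.78 should not be read as the power of the planned tests. Under the assumptions above, those tests have about 0.63 or 0.72 at full retention and about 0.58 or 0.67 at 20% loss. Attrition is the smaller cause; the number of schools per contrast is the larger.

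**What to change.** In the power paragraph of the Data Analysis Plan:

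- Say whether 1494 is the enrolled or the analysed number.
- State the expected retention at T3 and its source; the earlier FPNG trial, already used for the clustering parameters, is the natural one.
- Restate power for the planned FPNG+ contrasts (6 v 6 schools) at the retained number per school, for example about 66 at 80% retention, separately for T2 and T3.
- Name alpha, sidedness, the contrast and the reference distribution.

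Subtracting an attrition cost from 0.802 would not be enough, because that figure is not reproduced for the planned contrasts. The work is one recalculation and a few sentences, with no extra enrolment. The downside is a less favourable stated power.

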We will use both baseline adjusted general linear model procedures (i.e., variants of multiple regression) and latent change modeling to test intervention efficacy. In all models, because the FPNG Plus is the intervention condition of interest, all analyses will use FPNG Plus as the reference group. The two remaining conditions (FPNG and Comparison) will be compared with the reference group. The first method will predict short-term (T2) and then long-term (T3) post-test outcome measures (e.g., adolescents substance use and diet outcomes), while controlling simultaneously for the baseline (T1) measure of the particular outcome. Latent-change models³¹ will test whether and how changes over time in the outcomes differ significantly. Latent-change models will enable the assessment of change between T1 and T2 separately from change between T2 and T3. This examination will simultaneously test for improvements manifested during the course of the intervention (i.e., between T1 and T2) and for improvements maintained following the completion of the intervention (i.e., between T2 and T3). For mediation analyses, we will employ multivariate linear regression path analyses.^{32,33} Each mediation model will test the indirect path between the intervention condition at T1 and outcome measures at T3 (e.g., adolescents substance use and nutrition outcomes) mediated through family functioning, parenting strategies, and parents' social support at T2. Mediation models will control for baseline (T1) measures of the particular mediator and outcome. We will employ a bias-corrected bootstrap approach to test the indirect effect.³⁴

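### The stated power of 0.802 does not hold for the planned comparisons of 6 v 6 schools: the protocol's own inputs give about 0.63 to 0.72 at two-sided 5%

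*Combined protocol and SAP*

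**What the plan says.** The power paragraph of the Data Analysis Plan sets the size of the trial: "The total estimated sample size is 1494 parent-child dyads, across 18 schools". It gives an ICC of 0.01, a student-level R-square of 0.25 and a school-level R-square of 0.03. It sizes the trial on substance use because the effect expected there is the smaller one: "the effect size for substance use outcomes ($d=0.20$; FPNG vs. C"). It then concludes: "Accounting for these parameters, the power of this design is 0.802".

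Three other statements fix what is being tested:

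- Under Study design, schools are randomised and the curricula are delivered "in 18 different schools (6 per condition"), with 498 dyads per arm.
- The Data Analysis Plan makes FPNG+ the reference group: "The two remaining conditions (FPNG and Comparison) will be compared with the reference group".
- On estimation: "All analyses will employ a robust maximum likelihood estimator to adjust for any non-normality in the distributions of outcomes".

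The documents do not give the significance level, whether tests are one- or two-sided, the contrast to which 0.802 refers, the reference distribution, or a dropout rate.

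**The concern.** In a school-randomised trial, power depends mainly on the number of schools in the comparison. The paragraph speaks of 18 schools and 1494 dyads, but no planned contrast uses all of them. Each pairwise comparison has 12 schools and 996 dyads. That includes FPNG v Comparison, the source of d = 0.20, which is not one of the two planned contrasts.

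The 0.802 is the only justification given for the total sample size. If it does not describe the planned tests, the trial is more likely to miss the substance-use effect than its readers are told. A null result on that outcome would then be read as stronger evidence than it is.

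**Working it through.** **Inputs.** From the power paragraph: N = 1494, 18 schools, ICC = 0.01, student R-square = 0.25, school R-square = 0.03, d = 0.20 (outcome SD = 1). From Study design: 6 schools per arm. Assumed, because not stated: two-sided 5% and no attrition.

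**Dyads per school.** 1494 / 18 = 83.

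**Variance of an adjusted school mean.**
ICC × (1 − school R-square) + (1 − ICC) × (1 − student R-square) / 83
= 0.01 × 0.97 + 0.99 × 0.75 / 83
= 0.00970 + 0.00895 = 0.01865.

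**Standard error of a 6 v 6 difference.** sqrt(0.01865 × (1/6 + 1/6)) = 0.0788.

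**Noncentrality.** 0.20 / 0.0788 = 2.537.

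**Trying to reproduce 0.802.** No 6 v 6 calculation at two-sided 5% with the printed inputs reaches it. These variants come nearest:

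| Layout | Test | Power by t | Power by normal |
|---|---|---|---|
| 6 v 6 (planned) | two-sided 5% | 0.629 (10 df), 0.660 (15 df) | 0.718 |
| 6 v 6 | one-sided 5% | 0.763 (10 df), 0.781 (15 df) | 0.814 |
| 9 v 9 (18 schools as two arms) | two-sided 5% | 0.831 (16 df) | 0.874 |
| 12 v 6 (two arms pooled) | two-sided 5% | 0.785 (16 df) | 0.834 |

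The 10 df come from the 12 schools in one contrast (12 − 2). The 15 df come from fitting all three arms together (18 − 3). The normal column is the large-sample reference that robust maximum likelihood implies if no small-sample correction is made. It is optimistic here: its critical value is 1.96, against 2.13 for t on 15 df and 2.23 for t on 10 df.

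**Effect detectable with 80% power, 6 v 6, two-sided 5%.** 0.245 (10 df), 0.236 (15 df), 0.221 (normal).

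**Could a rounded ICC explain it?** Reaching 0.802 on 6 v 6 needs an ICC of 0.0034 (10 df), 0.0044 (15 df) or 0.0064 (normal). Only the last would print as 0.01, and it needs the normal reference. At an ICC of 0.005, the t results are still 0.76 and 0.79.

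**What 0.802 would take at ICC 0.01.** About 135 dyads per school (normal), or 207 (15 df) to 281 (10 df), against 83 planned.

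**If 1494 is the enrolled number.** With assumed losses by T3, two-sided 5% power on 6 v 6 becomes:

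| Assumed loss | t (10 to 15 df) | Normal |
|---|---|---|
| 10% | 0.61 to 0.64 | 0.70 |
| 20% | 0.58 to 0.61 | 0.67 |
| 30% | 0.55 to 0.58 | 0.64 |

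**The case against.** The strongest reply is that 0.802 is under-specified rather than shown to be wrong. The paragraph attaches it to the design as a whole and gives neither alpha nor sidedness. A one-sided 5% normal test on 6 v 6 gives 0.814, and an ICC of 0.0064 printed as 0.01 would give 0.802 by a two-sided normal test. The wording that suggests two-sided testing, "will test whether and how changes over time in the outcomes differ significantly", describes only the latent-change models, and the same part of the plan also speaks of testing for improvements. This stands so far as the cause goes: the documents do not show where 0.802 came from, and two-sided 5% is an assumption. It does not rescue the figure. The plan states no one-sided test, which by t would give only 0.76 to 0.78, and it says the ICC equals 0.01.

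A second reply is that the formula used here may not be the sponsor's. For the subsample (7 per school, effect 0.69) the plan states 0.814, whereas the same formula at 6 v 6 and two-sided 5% gives 0.885 to 0.940, above the stated figure. That is a fair caution about the origin of both numbers. But the alternatives that come near 0.802 give about 0.97 to 0.98 for the subsample, so the second figure supports none of them.

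A third reply concerns d. The introduction intends FPNG+ to keep FPNG's effect on substance use, so FPNG v Comparison is a natural stand-in for FPNG+ v Comparison. That is reasonable, though the plan should say so. For FPNG+ v FPNG, the documents claim no substance-use difference of 0.20, so the miss rate at 0.20 bears mainly on FPNG+ v Comparison.

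**Conclusion.** The concern holds. With the printed inputs and an assumed two-sided 5% level, a planned contrast has power of 0.63 to 0.66 by t, or 0.72 by the normal reference, where the plan claims 0.802. The chance of missing a true d = 0.20 is therefore 28% to 37%, not 20%. These figures allow nothing for attrition or for testing two contrasts. At two-sided 2.5% for each contrast, power would be 0.49 (10 df), 0.53 (15 df) or 0.62 (normal).

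The arithmetic is secure given the stated inputs; the cause of the discrepancy is not known. The points about attrition and the choice of d are missing detail, and the conclusion does not depend on them.

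**What to change.** In the power paragraph of the Data Analysis Plan:

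- Restate the power for the planned 6 v 6 contrasts, naming the contrast, alpha, sidedness and reference distribution. At two-sided 5%, d = 0.20 and 83 dyads per school, this is about 0.63 to 0.66 by t (0.72 by normal), with a detectable effect of 0.24 to 0.25 (0.22 by normal).
- Explain why d = 0.20, taken from FPNG v Comparison, is used for contrasts with FPNG+, and what difference, if any, is expected between FPNG+ and FPNG on substance use.
- Say whether 1494 is the enrolled or the analysed number. If enrolled, add the power for the dyads expected at T3.
- If 0.802 came from another layout, a one-sided test or an unrounded ICC, say so.

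This is a change of wording only, with no change in enrolment. Its one cost is a less favourable stated power.

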Self-identified Latino families (determined by their response on the survey question regarding ethnicity) with 6th, 7th or 8th grade children will be eligible to participate in an exploratory sub-study involving data collection through a home visit. To create the subsample of parents and youth who will participate in additional data collection for the exploratory aim, of those parents who choose to provide personal consent and child permission for surveys, for each of the three conditions, we will randomly select 9 self-identified Latino families per school (determined by their response on the survey question regarding ethnicity) to participate in all exploratory data collection procedures (finger prick; weight, height and blood pressure; 24 hour Food Recall; household food inventory). Because parents will have the choice to consent to these additional procedures, we will create a randomly selected mirror sample of an additional 9 self-identified families (determined by their response on the survey question regarding ethnicity) per school. If one of the original 9 parents chooses not to participate in these additional data collection procedures, we will randomly select a family from the mirror sample. This procedure will continue until we have 9 families per school (from each of all three conditions) who agree to participate

in all phases of data collection. Families in the mirror sample will not be contacted by the research team unless an original family chooses not to participate.

Data collection

Data collection from both parents and youth will take place at baseline (T1), immediately post-intervention at 10 weeks (T2), and at approximately 16 weeks post-intervention (T3). All parents and youth will be asked to complete a survey to collect information on substance use and nutrition outcomes (see Measures) regardless of intervention condition at the youth's school.

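### The main power of 0.802 and the subsample power of 0.814 do not both follow from the one set of clustering parameters given for them

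*Combined protocol and SAP*

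**What the plan says.** The Data Analysis Plan states the clustering inputs once: "an intraclass correlation equal to 0.01, a student level R-square of 0.25, and a school level R-square of 0.03". For the main design it adds an effect size of 0.20 for substance use, taken from FPNG against the comparison condition, and the sample: "The total estimated sample size is 1494 parent-child dyads, across 18 schools". It concludes: "Accounting for these parameters, the power of this design is 0.802".

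For the subsample, "the estimated sample size is 126 households across 18 schools", that is, 7 per school. The effect size is sourced as follows: "The average effect size of .69 is calculated based upon prior work on home food availability of vegetables, fruits, and desserts". The conclusion is "Given the above stated parameters, the power of this design is 0.814". No separate intraclass correlation or R-square is given for the subsample. Neither figure comes with an alpha, sidedness, degrees of freedom, contrast, number of schools per contrast or retention rate.

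Three other places bear on this. Study design puts six schools in each condition. The Data Analysis Plan makes FPNG+ the reference group and compares each other condition with it, so each test sets 6 schools against 6. Participant recruitment says of the home-visit families: "This procedure will continue until we have 9 families per school". That makes 9 × 18 = 162 families, while Data collection and the power paragraph both use 126.

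**The concern.** The wording presents both powers as results of the same parameters. The two designs share the schools and the randomisation and differ only in families per school and effect size, so their powers should stand in a fixed relation to each other. They do not.

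A reader relies on these two numbers to judge whether 18 schools are enough. If one basis cannot yield both, at least one rests on an input or a test that the plan does not disclose, and neither can be checked. The main figure matters more, because the total sample size was set on it.

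**Working it through.** **Inputs from the documents.** Intraclass correlation ρ = 0.01; student-level R-square 0.25; school-level R-square 0.03; 6 schools per arm; main design 1494/18 = 83 dyads per school with d = 0.20; subsample 126/18 = 7 families per school with d = 0.69.

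**Inputs assumed.** Two-sided alpha 0.05 and no loss to follow-up. Degrees of freedom are 10 (12 schools less 2) or 15 (18 schools less 3), with the normal approximation for comparison.

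**Formula.** For k schools per arm and n families per school:

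- V = ρ(1 − 0.03) + (1 − ρ)(1 − 0.25)/n
- SE = √(2V/k)
- noncentrality = d/SE, with power from the noncentral t

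**Step 1: the planned contrast, k = 6.**

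- Main: V = 0.0097 + 0.7425/83 = 0.01865; SE = 0.0788; noncentrality 2.537.
- Subsample, 7 per school: V = 0.0097 + 0.7425/7 = 0.11577; SE = 0.1964; noncentrality 3.512.
- Subsample, 9 per school: V = 0.0097 + 0.7425/9 = 0.0922; SE = 0.1753; noncentrality 3.936.

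| Design | Stated | 10 df | 15 df | Normal |
|---|---|---|---|---|
| Main, 83 per school | 0.802 | 0.629 | 0.660 | 0.72 |
| Subsample, 7 per school | 0.814 | 0.885 | 0.907 | 0.94 |
| Subsample, 9 per school | none | 0.943 | 0.957 | 0.98 |

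Neither stated figure is reproduced on this basis. The subsample figure is too low and the main figure too high.

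**Step 2: a comparison that does not depend on the number of schools.** In the ratio of the two noncentralities, k cancels:

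(0.69/0.20) × √(0.01865/0.11577) = 3.45 × 0.401 = 1.385.

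On 10 df, power 0.802 needs a noncentrality of 3.118 and power 0.814 needs 3.167, a ratio of 1.016. With the stated R-squares, therefore:

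- main 0.802 implies a subsample noncentrality of 3.118 × 1.385 = 4.32, power about 0.97;
- subsample 0.814 implies a main noncentrality of 3.167/1.385 = 2.29, power about 0.54.

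Other degrees of freedom give the same values to two decimals. A common loss of 15% or 20% lowers the ratio only to 1.34 or 1.32, and dropping both R-squares lowers it to 1.313. Across the variants tried at ρ = 0.01 (R-squares kept, dropped or swapped; other alphas; one-sided tests), the implied subsample power was 0.93 to 0.97 and the implied main power 0.54 to 0.65. A three-arm omnibus F test gave 0.52 to 0.53 for the main design.

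**Step 3: bases that come near one of the figures.**

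| Basis | Main | Subsample |
|---|---|---|
| All 18 schools as a two-group split, 15% loss, 16 df | 0.800 | 0.963 |
| 6 v 6 schools, 20% loss, 10 df | 0.581 | 0.814 |
| 6 v 6 schools, no R-squares, 15 df | 0.590 | 0.819 |
| Three-arm omnibus F, middle arm halfway, 14 to 15 df | 0.519 to 0.525 | 0.810 to 0.817 |

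Each comes near one stated figure and misses the other.

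**Step 4: minimum detectable effect in the subsample.** At 80% power and 10 df the multiplier is 3.11. This gives 3.11 × 0.1964 = 0.61 SD with 7 per school and 3.11 × 0.1753 = 0.55 SD with 9.

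**The case against.** The strongest reply is that 0.814 is not shown to be wrong. With so many inputs unstated, it lies within the range of ordinary choices. The omnibus F test in Step 3 uses every stated parameter and reaches 0.810 to 0.817. A pairwise contrast at two-sided 0.025 gives 0.793 on 10 df and 0.834 on 15 df, which bracket it. This stands: a reader might infer that the subsample figure is an arithmetic error, and the documents do not support that. It also does not rescue the pair. The omnibus test is not the planned analysis and needs the third arm exactly midway (about 0.91 if one arm alone differs). It also leaves the main design near 0.52.

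A reader might also infer that the two figures can share no basis at all. That is too absolute. With the intraclass correlation set to zero the ratio falls to 3.45 × √(7/83) = 1.002, and an unclustered, unadjusted test with an assumed 20% loss gives 0.806 and 0.807. But that discards every clustering parameter in the paragraph and contradicts its statement that design effects were considered.

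Third, a stated power below the computed one does not lead to an underpowered subsample. This stands.

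Last, a reader might infer that the plan claims 0.81 power for HbA1c, cholesterol, blood pressure and BMI. It does not: the effect size is tied to home food availability in the preceding sentence, and the sub-study is called exploratory. What remains is that the conclusion speaks of the design as a whole and would be clearer if limited to that outcome.

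**Conclusion.** The concern holds in a limited form. On any one clustered basis tried with an intraclass correlation of 0.01, the two stated powers are incompatible, so they do not both follow from the stated parameters. The Step 2 ratio does not depend on how many schools enter a contrast.

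On the planned contrast the subsample has about 0.885 to 0.91, against 0.814 stated, and the main design about 0.63 to 0.66 (0.72 by normal approximation), against 0.802 stated. These values assume two-sided 0.05, no loss and no multiplicity adjustment. On that basis the subsample figure is conservative and the main figure carries the consequential shortfall. The two figures may rest on different tests, alphas, retention rates or clustering inputs, and the documents do not show which unstated choice lies behind 0.814. The conflict between 7 and 9 families per school is real but does not explain it, since 9 per school raises the computed power to 0.94 to 0.96 on the t distribution.

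**What to change.** In the Data Analysis Plan, recompute both powers on one basis, the planned contrast of 6 against 6 schools. For each figure, state alpha, sidedness, degrees of freedom, assumed retention, and the intraclass correlation and R-squares used. If loss is built into one figure, apply it to the other.

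Reconcile 7 families per school (126 in all) with 9 (162 in all) across Participant recruitment, Data collection and the power paragraph, saying whether the difference is an allowance for loss.

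Label the subsample power as applying to home food availability only. For the other exploratory outcomes, give a minimum detectable effect: about 0.61 SD with 7 analysed families per school or 0.55 SD with 9, if the stated correlation and R-squares are taken to apply to them.

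Do not print 0.885 in place of 0.814 unless two-sided 0.05, 10 degrees of freedom, no loss and the stated clustering inputs are confirmed as the intended assumptions. The cost is recalculation and corrected text, with no change in enrolment.
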